11.3.4. Method of Reporting Adverse Events and Serious Adverse Events

11.3.4.1. Method of Reporting Adverse Events

Throughout the study, AEs will be documented on the source document and on the appropriate page of the eCRF whether or not considered treatment-related.

11.3.4.2. Method of Reporting Serious Adverse Events

Any SAE, including death resulting from any cause, which occurs to any participant participating in this study, must be reported via email or fax by the investigator using the Endo Serious Adverse Event (SAE)/Reportable Event Form within 24 hours of first becoming aware of the SAE. Follow-up information collected for any initial report of an SAE must also be reported to the sponsor within 24 hours of receipt by the investigator.

All Endo Serious Adverse Event (SAE)/Reportable Event Forms should be sent to [contact] or faxed to [contact].

The sponsor will determine whether the SAE must be reported within 7 or 15 days to regulatory authorities in compliance with local and regional law. If so, the sponsor (or the sponsor's representative) will report the event to the appropriate regulatory authorities. The investigator will report SAEs to the IRB per their IRB policy.

11.3.4.3. Follow-up Procedures for Serious Adverse Events

To fully understand the nature of any SAE, obtaining follow-up information is important. Whenever possible, relevant medical records such as discharge summaries, medical consultations, and the like should be obtained. In the event of death, regardless of cause, all attempts should be made to obtain the death certificate and any autopsy report. These records should be reviewed in detail, and the investigator should comment on any event, lab abnormality, or any other finding, noting whether it should be considered a serious or nonserious AE, or whether it should be considered as part of the participant's history. In addition, all events or other findings determined to be SAEs should be identified on the Serious Adverse Event (SAE)/Reportable Event Form and the investigator should consider whether the event is related or not related to study intervention. All events determined to be nonserious should be reported on the eCRF.

11.4. Appendix 4: Contraceptive Guidance and Collection of Pregnancy Information

See Section 6, Section 9.2.6, and Section 9.3.5.

11.5. Appendix 5: Liver Safety: Suggested Actions and Follow-up Assessments

All events, which may indicate severe liver injury (possible Hy's Law), meeting the following criteria:

- $ALT \geq 3 \times ULN$ or $AST \geq 3 \times ULN$ and $TBL \geq 2 \times ULN$ ($> 35\%$ direct bilirubin),
OR
- $ALT \geq 3 \times ULN$ or $AST \geq 3 \times ULN$ and $INR > 1.5$

must be reported as an SAE as outlined in Section [11.3.4](#).

Participants with confirmed Hy's Law liver injury will be immediately withdrawn from study intervention and no rechallenge will be allowed.

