
At the Day 29 visit, if the participant has any previously treated nodule(s) that remains palpable and measurable by caliper with a consistency of hard, firm throughout, moderately firm, or soft that is/are deemed appropriate for treatment by the investigator, and the Treatment 2 criteria are met a second dose of the study intervention may be administered.
 
For all participants, at the time points listed in the Schedule of Assessments, the efficacy of the study intervention will be assessed on the FFI (adapted for plantar fibromatosis; May 2021), the Subject Satisfaction with Treatment Scale, the PGIC PF Overall and individual PGIC subscales of pain, difficulty, and activity limitation, the Pain NRS, the PGIS PF Overall, and the individual PGIS subscales of pain, difficulty, and activity limitation, and the Clinician Global Impression of Change Scale. Safety will be assessed by evaluating the incidence and duration of TEAEs, AESIs, and SAEs, and changes in vital signs and clinical laboratory values.
 
All participants will complete the study on Day 57 (EOS Visit), regardless of whether they receive 1 or 2 treatments during the study. At the EOS visit, immunogenicity samples will be collected, safety will be assessed, and nodules will be measured. The maximum duration of participation is up to 85 days (Screening Period: 28 days, Treatment Period: 1 or 2 days, and a total Follow-up Period of 56 days).

Disclosure Statement: This is a placebo-controlled efficacy and safety study with 2 blinded treatment groups.
Number of Participants (planned): Participants will be screened to ensure that approximately 172 participants are randomized into 2 treatment groups, an EN3835 group and a placebo group in a 1:1 ratio.

Treatment Groups and Duration: There will be an active treatment group and a placebo treatment group of participants that receive up to 2 treatments of either EN3835 or placebo.
 
Duration of the study:
 
Screening Phase: Up to 28 days
 
Study Intervention Administration: Up to 2 days
 
Follow-Up Phase: from Intervention Administration 1 (End of Day 1) until Day 57 (\pm 5 days)
 
Total Duration of the Study: Up to 85 Days (\pm 5 days)

Independent Data Safety Monitoring Board: An independent unblinded data monitoring committee will review safety data periodically.

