2.3. Schedule of Assessments (Screening to End-of-Study)

	Screening D -28 to D -1	Treatment Visit 1 D1	Follow-up Visits			EOS/ET D57 (±5)	Safety Follow-Up ^s
			D15 (±1)	Treatment Visit 2 D29 (±1)	D43 (±1)		28 days after the last dose (+5)
Obtain signed informed consent ^a	X						
Inclusion/exclusion criteria	X	X ^b					
Treatment 2 criteria				X ^{b,c}			
Medical and surgical history ^d	X						
Prior medications and procedures	X						
Serum pregnancy test ^e	X					X	
Urine pregnancy test ^e		X ^b		X ^{b,c}			
Physical examination	X ^f					X	
Foot examination	X	X ^b	X	X ^b	X	X	
Clinical laboratory tests	X					X	
Immunogenicity sample collection ^g		X ^b				X	
Vital signs ^h	X	X ^{b,i}	X	X ^{b,i}	X	X	
Examination and evaluation of the selected nodule(s):							
a) Caliper measurements	X	X ^b	X	X ^b	X	X	
b) Foot Function Index (FFI) ^{j,k}	X	X ^b	X	X ^b	X	X	
c) Nodular consistency (palpation) ^l	X	X ^b	X	X ^b	X	X	
d) Nodular hardness measurement using a durometer	X	X ^b	X	X ^b	X	X	

	Screening D -28 to D -1	Treatment Visit 1 D1	Follow-up Visits			EOS/ET D57 (±5)	Safety Follow-Up ^s
			D15 (±1)	Treatment Visit 2 D29 (±1)	D43 (±1)		28 days after the last dose (+5)
e) Anatomical representation of nodule(s) location ^m	X	X ^b		X		X	
Patient Global Impression of Severity (PGIS) PF Overall Scale Pain, Difficulty and Activity Limitation Subscales ^k	X	X	X	X	X	X	
Patient Global Impression of Change (PGIC) PF Overall Scale Pain, Difficulty and Activity Limitation Subscales ^k			X	X ^b	X	X	
Pain Intensity Numerical Rating Scale (NRS) ^k	X	X	X	X	X	X	
Subject Satisfaction with Treatment Scale ^k			X	X ^b	X	X	
Clinician Global Impression of Change Scale			X	X ^b	X	X	
Randomization		X ⁿ					
Study intervention administration ^o		X		X ^p			
Concomitant medications and procedures ^q		Throughout the study					
Adverse events (AEs) ^r		Throughout the study					

- ^a Performed prior to any study-required assessments.
 - ^b Before treatment.
 - ^c The second treatment should be administered only if the participant has a previously treated palpable nodule measurable by caliper and the nodule (eg, hard, firm throughout, moderately firm or soft) is appropriate for a second treatment, according to the investigator. Women of childbearing potential must also have a negative urine pregnancy test (see Section 6.2.1). The participant must not have any significant medical conditions, which in the investigator's opinion would preclude receiving a second treatment (see Section 6.2.2).

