At the time of the interim analysis of EN3835-105 there were 24 total treatment-related AEs in the 0.6 mg/mL group, 16 treatment-related AEs in the 1.2 mg/mL group, and 15 treatment-related AEs in the 2.25 mg/mL group. All AEs were of mild to moderate intensity and most resolved within 21 days. The safety profiles, including the type (injection site reactions, including pain, bruising, swelling, and ecchymosis), intensity, and duration of the treatment related AEs were similar among treatment groups. It was concluded that all concentrations were equally safe and well tolerated.

Dose Selection

Rodent studies assessed the effects of intravenous injection of EN3835 directly into the systemic circulation. Dose-dependent liver toxicity was noted at exposures greater than or equal to 13 times the 2.7 mg of the maximum recommended human dose on a mg/kg basis (Study LAB 1007-1671). Since the proposed maximum total dose of EN3835 recommended for intralesional injection per treatment visit will be much lower than the intravenous injection administered in rodent studies, Endo considers the proposed dose will have no risk of systemic toxicity.

Based on the aforementioned data, it was concluded that in the interim analysis of Study EN3835-105, both the 1.2 and 2.25 mg/mL concentrations had a better treatment effect versus the lowest concentration, 0.6 mg/mL. Participants who received 2 injections of either 1.2 mg/mL or 2.25 mg/mL had a better treatment effect compared to those receiving 1 injection. A better treatment response on the FFI was observed in participants who received 2 injections of 2.25 mg/mL compared to those receiving 2 injections of 1.2 mg/mL. Overall, participants in the 2.25 mg/mL group had the best treatment responses as defined above. Paired with the nearly equivalent safety profile between the 2 concentrations, the 2.25 mg/mL concentration was selected to be used in the retreatment phase of Studies EN3835-105 and EN3835-222. The maximum total dose of EN3835 to be administered during this study when both feet are treated is 1.8 mg, and the maximum dose administered to a single foot is 1.35 mg when only 1 foot is treated, given that these were the maximum doses evaluated in Study EN3835-105.

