11. Any other significant medical condition(s), which in the investigator's opinion would make the participant unsuitable for enrollment in the study.
12. Is pregnant or plans to become pregnant.
13. Is breastfeeding, or is providing or plans to provide breast milk in any manner during the study.

Prior/Concomitant Therapy:

14. Received surgical or non-surgical treatment(s) (eg, steroid injection, transdermal/intralesional verapamil, radiation therapy, extracorporeal shock wave therapy) on the foot or nodule(s) to be treated within 3 months before administration of study intervention.
15. Has received any collagenase treatment (eg, Santyl[®] ointment, XIAFLEX[®]/XIAPEX[®], EN3835, or CCH) within 30 days prior to Day 1.
16. Is currently receiving, has received (within 7 days of the first treatment of study intervention, or plans to receive any anticoagulant or antiplatelet medication (except for ≤ 150 mg aspirin daily) that would increase the risk of bleeding during the study.

Prior/Concurrent Clinical Study Experience:

17. Participation in other studies involving an investigational drug within 30 days before treatment with study intervention and/or during study participation.
18. Has previously participated in clinical studies of EN3835 in plantar fibromatosis.

Other Considerations:

19. Is from a vulnerable population, as defined by the US Code of Federal Regulations (CFR) Title 45, Part 46, Section 46.111(b) and other local and national regulations, including but not limited to, employees (temporary, part-time, full-time, etc) or a family member of the research staff conducting the study, or of the sponsor, or of the contract research organization, or of the Institutional Review Board (IRB).

6.2.1. Participant Inclusion Criteria – Treatment 2

To be eligible to receive the second treatment, on Day 29, the participant must meet the following criteria:

Disease Characteristics:

1. The participant may receive additional treatment if the participant has a previously treated nodule(s) that remains palpable (eg, hard, moderately firm, firm throughout or soft) on clinical examination and measurable by caliper.
2. Women of childbearing potential must have a negative urine pregnancy test.

6.2.2. Participant Exclusion Criteria – Treatment 2

Medical Conditions:

1. The participant must not have any significant medical conditions, which in the investigator's opinion would preclude receiving a second treatment.

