8. DISCONTINUATION FROM STUDY INTERVENTION AND PARTICIPANT WITHDRAWAL

8.1. Discontinuation of Study Intervention or from the Study

In rare instances, it may be necessary for a participant to be permanently discontinued from study intervention by the investigator or the sponsor for safety, behavioral, or compliance reasons. Participants who request to discontinue from the study intervention or discontinue from the study prior to the Day 57 visit will be encouraged to complete the remaining study visits and evaluations and provide any additional follow-up information as required by the study. Participants who discontinue from the study intervention and do not agree to remain in the study for follow-up until Day 57, will be requested to complete an ET visit and if applicable the 28-day post-treatment Safety Follow-up Visit (or phone call if a visit is not possible) to determine the status of any ongoing AEs/SAEs or the occurrence of any new AEs/SAEs. The date of and reason for discontinuation of study intervention will be recorded.

Discontinuation of study intervention for abnormal liver function will be considered by the investigator when a participant meets one of the conditions outlined in Section [11.5](#).

If a clinically significant finding is identified after the start of study intervention, the investigator or a qualified designee will discuss with the sponsor to determine if the participant can continue in the study and if any change in management is needed.

Participants who discontinue study intervention will not be replaced according to the discretion of the sponsor and discussion as needed with investigator.

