3.14. Clinical Safety Laboratory Tests

Clinical laboratory tests will be performed by a designated central laboratory as per Table 20. Blood and urine samples will be collected for testing clinical laboratory parameters at Screening and the Day 57 Visit. Any new clinically significant laboratory abnormality observed, will be considered as an AE or SAE as appropriate.

Table 20: Change Clinical Safety Laboratory Parameters

Hematology	Biochemistry	Urinalysis
Hemoglobin	Glucose	Glucose
Hematocrit	Sodium	Protein
Red blood cell	Potassium	Specific gravity
White blood cell (WBC)	Calcium	pH
Platelets	Chloride	Ketones
WBC Differential	Carbon dioxide (CO ₂)	Bilirubin
Prothrombin time (PT)/International Normalized Ratio (INR)	Blood urea nitrogen	Urobilinogen
	Creatinine	Nitrite
	AST	Blood ^a
	ALT	Leukocytes ^a
	Gamma-glutamyl transferase (GGT)	
	TBL (direct bilirubin reflex if elevated)	
	Albumin	
	Alkaline phosphatase (ALP)	
	Total protein	

^a Microscopic examination will be performed if blood or leukocytes are detected.

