4.9.2. Clinical Laboratories and Vital Signs

4.9.2.1. Potentially Clinically Important Laboratory Values

Sponsor determined potentially clinically important (PCI) laboratory values are presented in [Table 22](#).

Table 22: Potentially Clinically Important Laboratory Criteria

Parameter	PCI Low: ≤Or =	PCI High: ≥ Than Or =
Hemoglobin (g/L)	100	190
Hematocrit (%)	30	60
Platelets (10 ⁹ /L)	100	650
ALT (U/L)		3×ULN
AST (U/L)		3×ULN
Creatinine (μmol/L)		200
BUN (mmol/L)		14

ALT=alanine transaminase; AST=aspartate transaminase; BUN=blood urea nitrogen; ULN=upper limit of normal

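### The Appendix 5 liver withdrawal rule has no scheduled laboratory result to act on between the Day 1 and Day 29 doses, and no planned SAP laboratory table counts its joint criteria by arm

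*Protocol*

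**What the plan says.** **The rule.** Protocol 11.5 defines possible severe liver injury as ALT or AST ≥3×ULN together with either TBL ≥2×ULN (more than 35% direct) or INR >1.5. Events meeting that definition must be reported as SAEs. Participants in whom Hy's Law injury is confirmed "will be immediately withdrawn from study intervention and no rechallenge will be allowed". Section 8.1 refers to the same appendix in different terms: "Discontinuation of study intervention for abnormal liver function will be considered by the investigator when a participant meets one of the conditions" it lists.

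**Dosing.** Per the synopsis, participants "receive up to 2 treatments of either EN3835 or placebo", on Day 1 and optionally on Day 29 (±1). The Treatment 2 criteria (6.2.1 and 6.2.2) require a treated nodule that is still palpable and measurable, a negative urine pregnancy test in women of childbearing potential, and the investigator's judgement: "The participant must not have any significant medical conditions, which in the investigator's opinion would preclude receiving a second treatment". They ask for no liver result.

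**Laboratory schedule.** SAP 3.14 states: "Blood and urine samples will be collected for testing clinical laboratory parameters at Screening and the Day 57 Visit". The protocol's Schedule of Assessments marks the same two columns, the second shared with early termination.

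**Analysis.** SAP 4.9.2.1 begins "Sponsor determined potentially clinically important (PCI) laboratory values are presented in" Table 22, which covers hemoglobin, hematocrit, platelets, ALT, AST, creatinine and BUN. SAP 7.7.4 adds descriptive summaries for hematology and chemistry, low/normal/high shift tables at Day 57, and participant listings.

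**The concern.** With at most two doses, a rule that bars rechallenge has one decision to act on: whether the Day 29 injection is given. What it can do there depends on the liver information that exists by that visit. If injury develops without symptoms after the first dose, nothing in the schedule would show it before the second. A reader of Appendix 5 is not told this, and the Treatment 2 criteria do not mention the appendix.

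The analysis has a related gap. An isolated transaminase rise and a rise combined with raised bilirubin or INR mean very different things, and the protocol singles out the second. If the laboratory flags cover transaminases only, the comparison of that event between arms has to be put together by hand from listings.

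**Working it through.** The plan states no figure on this point, so there is none to reproduce. The check is visit-window arithmetic and a comparison of two lists.

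**Step 1: scheduled panels between the doses.** Inputs from the Schedule of Assessments:

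| Event | Nominal day | Window |
|---|---|---|
| Screening panel | Day −28 to −1 | before any dose |
| Dose 1 | Day 1 | none |
| Dose 2 (optional) | Day 29 ±1 | Days 28 to 30 |
| Post-dose panel | Day 57 ±5 | Days 52 to 62 |

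Scheduled panels after Dose 1 and up to Dose 2: **0**.

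**Step 2: timing of the first scheduled post-dose panel, for a participant who stays in the study.**

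- After Dose 1: 52 − 1 = 51 to 62 − 1 = 61 days; nominal 57 − 1 = 56.
- After Dose 2: 52 − 30 = 22 to 62 − 28 = 34 days; nominal 57 − 29 = 28.

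An early-termination panel can come sooner, but only for someone who is already leaving. At the Day 29 visit the latest scheduled liver value is the Screening one, taken before any exposure.

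**Step 3: the rule's analytes against the SAP flags.**

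- Protocol 11.5 uses {ALT, AST, TBL, INR}.
- SAP Table 22 flags {hemoglobin, hematocrit, platelets, ALT, AST, creatinine, BUN}.
- In the rule but not flagged: {TBL, INR}, **2 of 4**.
- Joint criteria in 11.5: 2. Joint criteria tabulated: **0 of 2**.

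TBL and PT/INR are both collected (SAP Table 20). Protocol Exclusion Criterion 9 uses the same four limits at entry, so the protocol states each limit twice and the SAP flags carry over two of them.

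**Step 4: whether other planned tables give the joint count.** The shift tables treat one analyte at a time and have a single high category, so TBL just above ULN and TBL above 2×ULN fall in the same cell. Single-analyte counts also do not fix the overlap. If *a* of *n* participants in an arm reach the transaminase limit and *b* reach the TBL limit, the number with both can be anything from max(0, *a* + *b* − *n*) to min(*a*, *b*). For rare findings the lower end is 0. The joint count is therefore recoverable only participant by participant, from the listings.

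**Step 5: the two protocol wordings.** Section 8.1 leaves discontinuation to the investigator's consideration once a condition is met. Section 11.5 makes withdrawal immediate once injury is confirmed, under an appendix title that speaks of suggested actions. The two could be read as stages (possible, then confirmed), but neither section says so, and 11.5 does not say what confirmation consists of.

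**The case against.** The case on the other side is substantial.

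- **Unscheduled testing is allowed.** Protocol 9.2 permits safety assessments outside the schedule. Section 9.2.5 lets the investigator order further laboratory tests and gives out-of-range results and symptoms as examples of reasons. Adverse events are asked about at every visit (9.3.2), so at Day 15 and again at Day 29. Under 8.1, a clinically significant finding is discussed with the sponsor, and 6.2.2 lets the investigator withhold the second treatment. A reader might infer that the rule can stop nobody. That is not supported: a symptomatic participant can be tested and stopped before Day 29.
- **A conditional rule is compatible with sparse testing.** Withdrawal applies to confirmed injury only, and the study stopping rules in 5.2.4 contain no liver criterion. A reader might infer that the protocol promises a laboratory-based stop between doses. It does not.
- **The documents give a rationale for light monitoring.** Section 5.2.2 says "Dose-dependent liver toxicity was noted at exposures greater than or equal to 13 times the 2.7 mg", but this concerns intravenous dosing in rodents, and the sponsor concludes there that the proposed dose carries no systemic risk. Section 3.2.1 reports no quantifiable AUX-II exposure at total doses up to 1.8 mg. Entry criteria exclude abnormal liver values.
- **TBL and INR are not dropped from analysis.** A reader might infer that a Day 57 case would appear in the laboratory output only as an ALT or AST flag. That is wrong: both analytes are summarised, shift-tabulated and listed. Investigators review and sign laboratory reports, qualifying events must be reported as SAEs, and serious TEAEs are tabulated.

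All of this stands. It leaves two narrower points untouched: an asymptomatic case has no scheduled detection before the last dose, and no planned laboratory table counts the joint condition by arm. Whether testing should be denser is a clinical choice for the sponsor.

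**Conclusion.** The point holds in limited form. On scheduled data, no liver result is available between Day 1 and Day 29. For a participant who stays in the study, the first scheduled post-dose result comes 22 to 34 days after the second dose, when no study dose remains. Before then the rule works only through unscheduled, symptom-driven or discretionary tests. The protocol does not state this, and Sections 8.1 and 11.5 differ in wording.

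On the analysis side, two of the four analytes and both joint criteria are missing from the SAP's flags. This is a gap in tabulation. The data are collected and reported one analyte at a time.

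No event count can be attached. The documents give neither a retreatment rate nor an expected liver event rate, so the number re-dosed on EN3835 could lie anywhere from 0 to the planned 86, and the sponsor's own reasoning implies few or no cases. The conclusion rests on the visit windows as printed and on Table 22 and Section 7.7.4 as the full set of planned laboratory criteria. The table layouts in SAP Module 2 were not available.

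**What to change.** 1. **Protocol.** Reconcile Sections 8.1, 11.5 and 6.2.2 with the Schedule of Assessments, so that they say in one consistent way how the liver rule operates relative to the Day 29 dose. The sponsor decides how. If the existing arrangement is kept and described, the cost is wording, and the safeguard between doses will read as more limited than Appendix 5 now suggests. Any added draw would be an extra procedure, and this point does not ask for one.

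2. **SAP Table 22 and Section 7.7.4.** Add the protocol's own limits for TBL (≥2×ULN, with the direct-bilirubin condition) and INR (>1.5, a strict inequality where the table's column is ≥). Add the two joint Appendix 5 criteria, counted per participant by arm. State whether the components must come from the same sample and how unscheduled results are used. The central-laboratory data are already collected, so the cost is a few table rows and a footnote.
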